Concomitant medication	X	X	X			X	
AEs	X	X	X			X	
IXRS	X	X	X	X		X	X
Study drug sc onsite	X	X	X			X	
Study drug sc self-inj. at home					X		X
Telephone Contact ^k					X		X

Abs=antibodies; ADAb=anti-CZP antibody; AEs=adverse events; AS=ankylosing spondylitis; AsQoL=Ankylosing Spondylitis Quality of Life; BASDAI=Bath Ankylosing Spondylitis Disease Activity Index; BASFI=Bath Ankylosing Spondylitis Functional Index; BASMI=Bath Ankylosing Spondylitis Metrology Index; CRP=C-reactive protein; CZP=certolizumab pegol; EQ-5D=EuroQoL Health Status Questionnaire; H=home, no site visit; HN=home nurse visit at subjects home; IBD=Inflammatory bowel disease; IXRS=Interactive Voice or Web Response System; MASES=Maastricht Ankylosis Spondylitis Enthesitis Score; MRI=magnetic resonance imaging; PE=physical exam; sc=subcutaneously; SF-36=Short-Form 36-item Health Survey; TB=tuberculosis; W=Week

^a HN Q4W only for obtaining blood sample (CRP) and electronic patient reported outcome (ePRO) data as indicated

^b Schedule onsite visit every 12 weeks until Week 96 of regular visit schedule is reached. For example, at Weeks 74 and 86, if start of escape treatment is at Week 62 (=Escape Week 0). At Week 96 and SFU, perform assessments as described in [Table 5.1](#). For subjects experiencing a flare at/after Week 82, escape treatment should be provided for 12 weeks and the subject invited for the final assessment visit (as laid down for Week 96) 2 weeks later

^c Until 2 weeks before Week 96 of regular visit schedule is reached

^d Pulse rate, systolic and diastolic blood pressures, temperature, and respiration rate are to be measured at Screening and Baseline, thereafter pulse rate, systolic and diastolic blood pressures and temperature are to be measured. If a subject experiences an AE, respiration rate will be measured in addition

^e To be assessed as indicated and from Week 52 onwards every 4 weeks only

^f To be assessed every 4 weeks only (Weeks 8, 12, 16, 20, 24, ... up to Week 96)

^g To be assessed at escape Weeks 0 and 12 only

^h To be performed at escape Weeks 0 and 12 only and at final assessment visit at Week 96, if the last MRI was done at least 12 weeks prior to Week 96. Magnetic resonance imaging is to be performed within a ± 2 weeks time window.

[figure not shown]
ⁱ Occiput to wall distance; chest expansion; and BASMI, which includes modified Schober test, lateral spinal flexion, cervical rotation, tragus to wall distance, and maximal intermalleolar distance

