6.3.2 Escape treatment

Subjects receiving placebo or half-dose CZP (200mg Q4W) who experience a flare during the Double-Blind Period will escape to full-dose treatment (CZP 200mg Q2W) until the end of that period or for at least 12 weeks, whichever is longer. The escapers need to come back to the site at the timepoint of the escape (Week 0), 2 and 4 weeks after escape (Weeks 2 and 4), and every 12 weeks thereafter until the originally scheduled Week 96.

Subjects escaping from placebo to full-dose CZP (200mg Q2W) will receive a loading dose of CZP (400mg Q2W; 2 injections) at the 3 consecutive visits after the flare. Subjects escaping

from half-dose CZP to full-dose CZP will receive a loading dose of CZP 200mg Q2W at the 3 consecutive visits after the flare. In order to maintain the blind, subjects escaping from half-dose CZP to full-dose CZP will receive a placebo administration and a CZP 200mg administration (a total of 2 injections) at these 3 visits ([Figure 7.1](#)).

Subjects randomized to the CZP full-dose (200mg Q2W) treatment during the Double-Blind Period who qualify for escape will remain on their current treatment allocation. As with subjects escaping from half-dose CZP to full-dose CZP, these subjects will receive a placebo and CZP 200mg injection (a total of 2 injections) at the 3 visits after the flare in order to maintain the blind to the randomized treatment.

After the loading dose (200mg Q2W or 400mg Q2W), all escaped subjects will continue full-dose CZP treatment in an open-label fashion.

The definition of flare is provided in [Section 3](#).

At the Investigator's discretion, the subject may be withdrawn from the study at any time (eg, to receive alternative treatment for the disease).

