14.3.2.2 Part B analysis

The time to flare will be analyzed using Kaplan-Meier methods. For those who meet the criteria for flare, the time will be defined as the length in days from randomization in Part B until the visit at which the criteria for flare were met. Subjects who discontinue the study without meeting the criteria for flare will be censored at the time of their last study visit. Subjects who complete the study without meeting the criteria for flare will be censored at their Week 96 visit. Between group differences will be analyzed with the log-rank statistic.

The changes from Baseline in ASDAS, BASDAI, BASFI, and BASMI at Week 96 for the RS will be compared between treatment groups using a mixed model for repeated measures (MMRM). The pattern of missingness for these variables is assumed to be missing at random (MAR). Subjects who enter Part B will have already demonstrated sustained remission through 48 weeks on CZP 200mg Q2W. Many of these subjects will be randomized to receive placebo and will, therefore, be more likely to experience a flare. Postflare data for subjects who experience a flare (in any treatment group) will be treated as missing for the MMRM analysis. It is further assumed that most subjects who discontinue at this late stage in the study (ie, during Part B) will do so as a result of reduced efficacy. Therefore, missing efficacy data due to either flare or study treatment discontinuation should be dependent on the observed efficacy scores, but independent of unobserved data.

The MMRM model will include Baseline score as a fixed-effect covariate, treatment group, region, mNY criteria (yes/no), and visit as fixed-effect categorical factors, and Baseline-by-visit and treatment group-by-visit as interaction terms. An unstructured correlation pattern will be used to estimate the variance-covariance of the within-subject repeated measures. Tables will present the adjusted means for placebo and the CZP doses (200mg Q2W and 200mg Q4W), the respective difference to placebo, the corresponding p-value, and 95% CI.

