Change from Baseline in SIJ SPARCC and spine ASpIMRI-a in the Berlin modification scores at Week 96 will be compared between treatment groups using analysis of covariance (ANCOVA) for observed values only (ie, no imputation). The model will include Baseline score, treatment group, region, and mNY criteria (yes/no). Tables will present the adjusted means for placebo and the CZP doses (200mg Q2W and 200mg Q4W), the respective difference to placebo, the corresponding p-value, and 95% CI.

The binary secondary efficacy variables (ASDAS-MI, ASDAS-CII, ASAS20, ASAS40, ASAS5/6, ASAS PR, and BASDAI50 response) at Week 96 will be analyzed using a logistic regression. The odds ratio of the responder rates at Week 96 will be estimated and tested

between treatment groups using a logistic regression model with factors of treatment group, region, and mNY criteria (yes/no). Tables will present the responder rates for placebo, CZP 200mg Q2W, and CZP 200mg Q4W, the respective effect estimates (adjusted odds ratio with reference to placebo), p-values, and 95% CIs. Subjects with a missing responder status at Week 96 will be treated as a nonresponder for analysis purposes (ie, NRI).

Ankylosing Spondylitis Disease Activity Scores (ASDAS-ID, ASDAS-MD, ASDAS-HD, ASDAS-vHD) will be summarized by treatment group using summary statistics (counts and percentages) based on observed case data.

In addition to the analyses mentioned above, descriptive statistics (number of available observations [n], mean, median, SD, minimum, and maximum) will be provided by treatment group for the secondary efficacy variables. The descriptive analyses will be covered in the tables summarizing the variables over time. This will include a summary of the actual values, change from Baseline (Week 0), and change from randomization Baseline (Week 48). The statistical comparisons described for secondary efficacy variables are not part of the multiplicity-controlled testing procedure described in [Section 14.2](#). The p-values reported for these analyses will not be adjusted for multiplicity and will be considered nominal. All analyses and summaries of secondary efficacy variables in Part B will be based on the RS.

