14.3.3.2 Part B

Treatment group comparisons for both CZP groups vs placebo will be performed based on the change from Baseline in other selected efficacy variables. These analyses will be performed using an ANCOVA model with variables of Baseline score, treatment group, region, and mNY criteria (yes/no) in the model. The treatment differences and corresponding 95% CIs will be calculated based on the adjusted means. Missing values will be imputed using LOCF. This analysis approach will be used for the following variables:

- Total spinal pain
- Nocturnal spinal pain
- PtGADA
- Morning stiffness (BASDAI 5 and 6)
- SF-36 PCS, MCS, and physical function domain
- Fatigue NRS
- ASQoL

Such analyses will also be done for the following continuous variables: ASDAS, BASDAI, BASFI, and BASMI will be analyzed using a MMRM similar to the one specified in [Section 14.3.2.2](#) at timepoints not covered in the secondary efficacy analyses. Additionally, ASDAS-MI, ASDAS-CH, ASAS, and BASDAI50 response variables will be analyzed using a logistic regression model similar to the one specified for binary response variables in [Section 14.3.2.2](#) at timepoints not covered in the secondary efficacy analyses.

These comparisons are not part of the multiplicity-controlled testing procedure described in [Section 14.2](#). The p-values reported for these analyses will not be adjusted for multiplicity and will be considered nominal. Exploratory statistical comparisons will also be performed for WPS scores using the nonparametric bootstrap-t method. This will be explained in greater detail in the SAP.

All other efficacy variables will be summarized descriptively by visit and treatment group using observed case and imputed data based on the RS.

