14.6 Handling of dropouts or missing data

For the primary efficacy variable (percentage of subjects in Part B who do not experience a flare), an approach based on the principles of NRI will be used to impute missing values. Specifically, if a subject withdraws from Part B at any point, they will be considered as having not responded to treatment. Therefore, they will be assumed to have experienced a flare during Part B for analysis purposes. If a subject has an intermittent missing ASDAS score (ie, a missing value at 1 visit but nonmissing values at the previous and subsequent visit), then the missing value will be ignored and flare will be based on the 2 available values. If the ASDAS score is missing at 2 or more consecutive visits, then the subject will be treated as having experienced a flare (even if ASDAS scores are available after the missed visits).

For the time to flare endpoint, the rules as described above for the primary endpoint will be applied to account for missing data when determining whether or not a subject experienced a flare. Subjects who discontinue the study without meeting the criteria for flare will be censored

at the time of their last study visit. Subjects who complete the study without meeting the criteria for flare will be censored at their Week 96 visit.

Selected continuous secondary efficacy variables will be analyzed using MMRM methods (see [Section 14.3.2.2](#) for details). Missing data for binary response secondary efficacy variables will be handled using NRI. Secondary variables related to MRI will be analyzed based on the observed case data.

In general, other efficacy variables will be summarized as both observed case and with imputation (NRI for binary response variables and LOCF for continuous variables), unless otherwise specified. Nonresponse imputation is implemented by treating missing data for binary response variables as a nonresponse. The LOCF summaries will impute missing continuous data using the last post-Baseline nonmissing result. In the event that a subject has no post-Baseline data for a given continuous variable, no imputation will be performed.

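### As written, the seven binary Week 96 secondary responses score flared placebo and half-dose subjects on values obtained after they restarted full-dose CZP, which attenuates the nominal odds ratios against placebo.

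*Protocol*

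**What the plan says.** Section 14.3.2.2 names "The binary secondary efficacy variables (ASDAS-MI, ASDAS-CII, ASAS20, ASAS40, ASAS5/6, ASAS PR, and BASDAI50 response) at Week 96", seven in all, and compares the arms by logistic regression on treatment, region and mNY status. The population is fixed there: "All analyses and summaries of secondary efficacy variables in Part B will be based on the RS". The only rule for scoring nonresponse is "Subjects with a missing responder status at Week 96 will be treated as a nonresponder for analysis purposes (ie, NRI"). Section 14.6 repeats it in general form: "Nonresponse imputation is implemented by treating missing data for binary response variables as a nonresponse". Neither section gives these variables a rule for flare or escape.

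The continuous variables in Section 14.3.2.2 are handled differently: "Postflare data for subjects who experience a flare (in any treatment group) will be treated as missing for the MMRM analysis".

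Under Section 6.3.2, subjects on placebo or half dose who flare "will escape to full-dose treatment (CZP 200mg Q2W) until the end of that period or for at least 12 weeks, whichever is longer". Their Week 96 data are still collected. Footnote b of Table 5.2 (Section 5.2) reads "At Week 96 and SFU, perform assessments as described in" Table 5.1, and flares at or after Week 82 lead to a delayed final visit with the same assessments (Sections 5.2 and 8.5).

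Section 14.3.3.2 analyses further continuous variables, including PtGADA, morning stiffness and fatigue, by ANCOVA: "Missing values will be imputed using LOCF". It states no post-flare exclusion for them.

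**The concern.** A placebo subject who flares, restarts full-dose CZP and attends Week 96 does not have a missing status, so nonresponse imputation does not reach that subject. Read literally, the plan lets a response obtained on full-dose CZP count as a placebo response. The same happens in the half-dose arm.

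The section is then inconsistent with itself. Change in ASDAS and BASDAI drops post-flare data, while ASDAS-MI, ASDAS-CII and BASDAI50, derived from the same scores at the same visit, keep them. The gap recurs in Section 14.3.3.2: the LOCF ANCOVAs of PtGADA, morning stiffness and fatigue retain post-escape values, while the ASDAS and BASDAI models that contain those items do not.

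At stake is the reading of seven named secondary endpoints, each reported with an odds ratio, confidence interval and p-value. They would understate the effect of withdrawal and could seem to conflict with the primary result.

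**Working it through.** **The protocol's own power figures.** Section 14.8 assumes flare-free rates of 80% (full dose), 75% (half dose) and 45% (placebo), with 70 per arm and two-sided alpha 0.05, and states 98% and 94% power against placebo. The pooled normal formula is Φ[(d − 1.96·√(2p̄(1−p̄)/n)) / √((p₁q₁+p₂q₂)/n)], where d is the difference, p̄ the mean of the two rates and q = 1 − p. It gives 99.4% and 96.0%. With continuity correction the figures are 98.9% and 94.1%; Fisher's exact test gives 98.9% and 94.0%. The stated figures are reproduced.

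**Planned flares.** 70 × 0.55 = 38.5 placebo, 70 × 0.25 = 17.5 half dose, 70 × 0.20 = 14 full dose.

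**Weeks back on full dose.** Escape Week 0 is two weeks after the qualifying assessment, or earlier at the investigator's discretion (Section 5.2). For a flare at Week f, time on full dose at calendar Week 96 is 96 − (f + 2) = 94 − f.

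| Flare visit | Weeks on full dose at calendar Week 96 | Final visit | Weeks on full dose at final visit |
|---|---|---|---|
| 50 | 44 | 96 | 44 |
| 72 | 22 | 96 | 22 |
| 80 | 14 | 96 | 14 |
| 84 | 10 | 100 | 14 |
| 88 | 6 | 104 | 14 |
| 92 | 2 | 108 | 14 |

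For late flares the final visit follows 12 weeks of escape dosing plus 2 weeks, as in the Section 8.5 example (Escape Week 0 at Week 84, final visit at Week 98). The protocol does not say whether the delayed visit or calendar Week 96 supplies the Week 96 status.

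**Effect on the comparison.** Let S be the flare-free rate, a the response among non-flarers and b the response among retreated flarers. The protocol gives neither a nor b. I take a = 0.9 and b = 0.5, 0.7 or 0.9, the same b in all arms, with every planned flarer observed at the final visit. Arm rate = S·a + (1 − S)·b.

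| Scoring of flarers | Full dose | Half dose | Placebo | Full minus placebo | Power |
|---|---|---|---|---|---|
| Nonresponse | 72% | 67.5% | 40.5% | 31.5 points | 97% |
| Observed, b = 0.5 | 82% | 80% | 68% | 14 | 48% |
| Observed, b = 0.7 | 86% | 85% | 79% | 7 | 19% |
| Observed, b = 0.9 | 90% | 90% | 90% | 0 | no difference to detect |

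Power uses the pooled formula above.

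**Late flares scored as nonresponse.** Assume exponential flare times. The share flared by Week 80 is 1 − S^(32/48): 13.8% on full dose and 41.3% on placebo. The difference is (0.72 + 0.138b) − (0.405 + 0.413b) = 0.315 − 0.275b, which is 18, 12 and 7 points at b = 0.5, 0.7 and 0.9.

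**Sensitivity to a and to equal recovery.** With a = 1.0, 35 points falls to 17.5, 10.5 and 3.5 (power 99% falls to 76%, 50% and 19%). If full-dose flarers, whose CZP regimen does not change, recover half as often as retreated placebo flarers, then at a = 0.9 and b = 0.7 the rates are 79% and 79%. At b = 0.9 they are 81% on full dose and 90% on placebo, and the sign reverses.

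**The case against.** **The SAP may settle it.** Section 14 defers detail to the SAP, which was not available here, and the protocol nowhere says in words that post-escape values count as responses. But the point is not left open. A missing-only rule is stated in two sections and the post-flare exclusion is confined to the MMRM, so an SAP flare rule would change stated text.

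**Post-flare summaries use the Flared Set.** Section 14.3.2.3 places summaries after flare in the Flared Set on observed data. That governs the separate Escape Week 12 summaries. It does not make those data missing in the Randomized Set models.

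**Observed status is a legitimate treatment-policy comparison.** It is, but the protocol does not declare it, and it conflicts with the MMRM rule in the same section. Retreatment already has its own analysis. It is also fair that scoring flare as nonresponse brings these endpoints close to the primary and is not the same handling as missing-at-random in the MMRM.

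**The illustration is an upper bound on exposure.** This stands. The 55% placebo flare rate belongs to a primary variable that counts withdrawals and two consecutive missing visits as flare. If the 55% includes withdrawals, those without a Week 96 status are already nonresponders.

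**Stronger readings that a reader might infer and the documents do not support.**
- That every escaper has at least 14 weeks on full dose: this fails at calendar Week 96 for flares at Weeks 84, 88 and 92.
- That the withdrawal effect is erased: with equal recovery across arms, this needs retreated flarers to respond as often as non-flarers and final-visit values to be used.
- That the placebo response rate must jump between Week 84 and Week 96: Table 5.2 collects BASDAI, CRP and PtGADA every four weeks during escape, so several responses have values near Week 84.
- That the trial's main conclusion is at risk: the primary endpoint does not use these rules.

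**Conclusion.** The concern holds as an attenuation and a consistency problem. Following the text, flared placebo and half-dose subjects contribute responses obtained on restarted full-dose CZP to their randomised arm. The odds ratios against placebo are pulled toward 1 and disagree in handling with the MMRMs of the same scores. Under the stated assumptions the full-dose versus placebo difference is roughly halved or worse. The exact size is unknown, because the protocol gives no response rate for flarers or non-flarers and says only that retreatment generally worked well in earlier studies (Section 2.5).

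This should be fixed, but it is not critical. Sections 14.3.2.2 and 14.3.3.2 call these p-values nominal and place them outside the multiplicity procedure.

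**What to change.** 1. In Sections 14.3.2.2 and 14.6, and for the logistic models of Section 14.3.3.2, state that a subject in any arm who met the flare criteria at or before a visit is a nonresponder at that visit and at all later visits.
2. In the Section 14.3.3.2 ANCOVAs, set post-flare values to missing and analyse these variables with the same MMRM as ASDAS and BASDAI instead of LOCF.
3. Keep the observed-status Week 96 rates as a supportive table labelled as a treatment-policy comparison (withdraw or reduce, then retreat on flare), and say whether the delayed final visit supplies the Week 96 value for late flares.

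The cost is a few sentences and one derivation rule; no new data are needed. The downside is that full-dose subjects who flare and recover on unchanged treatment count as nonresponders, at most about 14 expected (20% of 70). That is in line with the primary endpoint, where a flare is already a failure.

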14.3.2 Analysis of the secondary efficacy variables

14.3.2.1 Part A analysis

The secondary efficacy variables defined in Part A are as follows:

- Percentage of subjects achieving sustained remission at Week 48
- ASDAS disease activity (ASDAS-ID and ASDAS-MD, ASDAS-HD, ASDAS-vHD) at Week 48
- ASDAS clinical improvement (ASDAS-MI and ASDAS-CII) at Week 48

The percentage of subjects achieving sustained remission, ASDAS-MI, and ASDAS-CII at Week 48 will be summarized using descriptive statistics (counts and percentages). Separate summaries will be done using NRI and observed case data.

Ankylosing Spondylitis Disease Activity Score disease activity at Week 48 will also be summarized using descriptive statistics, where counts and percentages are reported for each of the 4 categories. Two summaries will be provided: One will derive disease activity at Week 48 using last observation carried forward (LOCF, impute using the last post-Baseline nonmissing result) for missing values and the other will be based on observed case data.

All summaries of secondary efficacy variables in Part A will be based on the OLS.

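### The secondary Week 96 table of ASDAS disease-activity states uses observed cases only, while ASDAS-MI, ASDAS-CII and ASAS PR at the same visit use NRI, so the ASDAS-ID percentage tends to read too high

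*Protocol*

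**What the plan says.** Protocol Section 4.1.2.2 lists the ASDAS states (ID, MD, HD, vHD) and the ASDAS improvement variables (CII, MI) in a single bullet as secondary variables at Week 96. Section 9.1.7 derives all of them from one score, with ASDAS-ID defined as a score below 1.3.

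Section 14.3.2.2 then separates them. "The binary secondary efficacy variables (ASDAS-MI, ASDAS-CII, ASAS20, ASAS40, ASAS5/6, ASAS PR, and BASDAI50 response) at Week 96" go into a logistic regression, with this rule for gaps: "Subjects with a missing responder status at Week 96 will be treated as a nonresponder for analysis purposes (ie, NRI". Section 14.6 repeats the rule: "Missing data for binary response secondary efficacy variables will be handled using NRI". The four states are treated differently. They "will be summarized by treatment group using summary statistics (counts and percentages) based on observed case data", and the section names no imputed companion. It also states that "All analyses and summaries of secondary efficacy variables in Part B will be based on the RS".

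In Part A the same four states get two summaries (Section 14.3.2.1): "One will derive disease activity at Week 48 using last observation carried forward", and a second uses observed cases.

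On why subjects leave Part B, Section 14.3.2.2 assumes that "most subjects who discontinue at this late stage in the study (ie, during Part B) will do so as a result of reduced efficacy".

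**The concern.** An observed-case percentage describes the subjects who still have a score. If those without one are mostly treatment failures, as the protocol presumes, the ASDAS-ID percentage is calculated after removing people who would mostly have counted against it. The report would then show ASDAS-ID beside ASDAS-MI, ASDAS-CII and ASAS PR at the same visit on different denominators. ASAS PR is the closest comparison. It is also a state rather than a change (Section 9.1.1), and it is analysed with NRI.

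Every randomized subject had an ASDAS below 1.3 in the Week 48 qualification (Section 3). Readers will therefore look at the share still below 1.3 at Week 96 in each arm as a description of how well inactive disease is kept. What is at stake is the reading of that description and of the gap between arms. No hypothesis test is involved.

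**Working it through.** **Inputs.** The protocol states neither an expected ASDAS-ID rate nor a Part B withdrawal rate, so it has no figure of its own on this point to reproduce. Section 14.8 gives 70 subjects per arm, used here as the RS denominator. Every rate and missing percentage below is an assumption.

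**Formula for one arm.** Let n be the number randomized, m the number without a Week 96 score and k the number observed in ASDAS-ID.

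- Observed-case rate = k/(n − m)
- NRI rate = k/n
- Ratio = n/(n − m), which exceeds 1 whenever m > 0

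With n = 70 and about 60% of those observed in ASDAS-ID:

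| Missing | m | k | Observed case | NRI | Excess (points) | Ratio |
|---|---|---|---|---|---|---|
| 5% | 4 | 40 | 40/66 = 60.6% | 40/70 = 57.1% | 3.5 | 1.06 |
| 10% | 7 | 38 | 38/63 = 60.3% | 38/70 = 54.3% | 6.0 | 1.11 |
| 15% | 10 | 36 | 36/60 = 60.0% | 36/70 = 51.4% | 8.6 | 1.17 |
| 20% | 14 | 34 | 34/56 = 60.7% | 34/70 = 48.6% | 12.1 | 1.25 |

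At exactly 5% missing the ratio is 1/0.95 = 1.05; the table shows 1.06 because 4 of 70 is slightly more than 5%. If 40% to 80% of those observed are in ASDAS-ID, the excess runs from 2.3 to 4.6 points at 5% missing, 4.0 to 7.9 at 10% and 7.9 to 16.1 at 20%.

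**When the excess is bias.** NRI assumes that no missing subject is in ASDAS-ID. Let w be the missing fraction, p the observed-case rate and r the true ASDAS-ID share among the missing. The rate in all randomized subjects is p(1 − w) + rw, so the observed-case rate is too high by w(p − r). With w = 10% and p = 60%:

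- r = 0: 0.10 × 0.60 = 6 points
- r = 30%: 0.10 × 0.30 = 3 points
- r = 60%: none

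The protocol's premise about discontinuation puts r below p, which fixes the direction. It does not put r at zero.

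**Contrast between arms.** Assume observed-case rates of 65% (full dose) and 50% (placebo), a difference of 15 points. With 70 per arm the standard error is √(0.65 × 0.35/70 + 0.50 × 0.50/70) ≈ 8.3 points. Counting the missing as not in ASDAS-ID:

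| Missing, full dose | Missing, placebo | Full dose | Placebo | Difference (points) | Shift |
|---|---|---|---|---|---|
| 5% | 5% | 0.65 × 0.95 = 61.75% | 0.50 × 0.95 = 47.5% | 14.25 | −0.75 point |
| 5% | 10% | 61.75% | 0.50 × 0.90 = 45% | 16.75 | +1.75 points, 0.2 SE |
| 5% | 15% | 61.75% | 0.50 × 0.85 = 42.5% | 19.25 | +4.25 points, 0.5 SE |
| 5% | 20% | 61.75% | 0.50 × 0.80 = 40% | 21.75 | +6.75 points, 0.8 SE |

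With clearly more withdrawal on placebo, the observed-case table understates the difference. With equal withdrawal it overstates it slightly.

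**The case against.** **An imputed table may already be planned.** Section 4.1.3.2 lists the same states again as other Part B variables at all scheduled visits. Section 14.3.3.2 says that remaining other variables are summarized both as observed and as imputed on the RS, and Section 14.6 says much the same. This largely stands: a reader might infer that Part B has no imputed version at all, and the text does not support that. However, the rule for a four-category state is not named there, and Section 14.3.2.2 still fixes the secondary Week 96 summary as observed case. If the unnamed rule is LOCF, a subject who leaves before any Part B score would carry forward the qualifying value below 1.3 and count as ASDAS-ID.

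**Missing scores may be few.** Section 6.3.1 requires withdrawn subjects to attend a withdrawal visit with full assessments. The combined Week 96/WD column of Table 5.1 includes the ASDAS components. The protocol does not say whether such a score counts as Week 96. Flaring subjects are also offered escape treatment within the study. Both could shrink the effect, so a reader should not take 1/(1 − withdrawal rate) as a certain inflation factor. It holds only if every withdrawn subject lacks a Week 96 score and none is in ASDAS-ID.

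**Different variable types can have different rules.** MI and CII are tested binary responses. The states are an untested four-category description, and NRI has no direct meaning across four categories. That is fair, and the difference is not a contradiction. ASDAS-ID taken alone is binary, though, and the full table can carry a missing row. Since counts are shown, a reader can also divide by the number randomized.

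**The primary endpoint is the more direct reading of maintained response.** It already counts every Part B withdrawal as a flare (Sections 14.3.1 and 14.6). This stands. ASDAS-ID at Week 96 may also include flared subjects re-treated with full dose, a separate matter that the denominator does not settle.

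**Part A.** One might infer that no rule in the plan ever places a withdrawn subject outside ASDAS-ID. That is not so: LOCF at Week 48 does so whenever the last score is 1.3 or higher.

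**Conclusion.** The point holds as a small improvement to a descriptive table. Section 14.3.2.2 sets an observed-case rule for the secondary Week 96 ASDAS states beside an NRI rule for variables from the same score and visit. On the protocol's own premise about discontinuation, this tends to make the ASDAS-ID percentage too high. Under an assumed 5% to 20% missing, with no missing subject in ASDAS-ID, the observed-case rate is about 1.05 to 1.25 times the NRI rate. In the illustrated contrasts the shift stays below one standard error, and with equal 5% withdrawal it is under 1 point.

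The size cannot be stated more firmly, because the protocol gives no Part B withdrawal rate and no mapping for withdrawal-visit scores. The documents do not support reading this as a threat to the trial's conclusions: no test, p-value, multiplicity claim or primary result depends on the table.

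**What to change.** In Section 14.3.2.2:

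- Present the Week 96 ASDAS-state table on all RS subjects, with a missing/withdrawn row in the denominator.
- Report ASDAS-ID (yes/no) at Week 96 with the NRI rule already used for ASDAS-MI and ASDAS-CII.
- Keep the observed-case table as supportive.

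A matching change for Week 48 in Part A is optional. Section 14.3.2.1 already summarizes sustained remission with NRI and the states with LOCF.

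The cost is a short wording change, one extra table row and the ASDAS-ID line, with slightly lower ASDAS-ID rates. No new data are needed.
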